### Table 16: Supplemental Endpoints - comparison: 50/28mg versus CS3B sham control

Endpoint and Comparison	Analysis Method	Analysis Population: further notes
-------------------------	-----------------	--

Product: Nusinersen Study: 232SM203		Statistical Analysis Plan Version: 3.0 Final
CHOP INTEND: Change from baseline to Day 64, accounting for mortality/dropout	Joint rank using multiple imputation (MI)	Matched Sham Set
Proportion of Motor Milestones	Logistic regression or	Matched Sham
responders at Day 64	Fisher's Exact Test	Set
The Proportion of CHOP INTEND	Logistic regression or	Matched Sham
Responders at Day 183	Fisher's Exact Test	Set

### 6.5.2. Comparison: 50/28mg versus 12 mg Group from 232SM203

For the comparison of higher dose and 12 mg Group from 232SM203, some of the secondary endpoints will be repeated as listed below, also the proportion of CHOP INTEND responders at Day 183 and Day 302 and proportion of Motor Milestones responders at Day 302 will be analyzed.

Endpoint Ar	alysis Method	Analysis Population: further notes
Change in CHOP INTEND from baseline to Day 18.	3 Joint rank using multiple imputation (MI)	ITT set Repeat for Day 29 and 64.
Change in Motor Milestones total score from baselin to Day 183	e Joint rank using multiple imputation (MI)	ITT set
The Proportion of CHOP INTEND Responders at Da 183	ay Logistic regression or Fisher's Exact Test	ITT set

### Table 17: Supplemental endpoints 50/28mg versus 12 mg Group from 232SM203

Product: Nusinersen	Statis	tical Analysis Plan
Study: 232SM203		Version: 3.0 Final
The Proportion of CHOP INTEND Responders at Day 302	Logistic regression or Fisher's Exact Test	ITT set
Proportion of Motor Milestones responders at Day 302	Logistic regression or Fisher's Exact Test	ITT set

Product: Nusinersen	Statistical Analysis Plan
Study: 232SM203	Version: 3.0 Final

## 6.6. Analysis of the Remaining Secondary Endpoints - comparison: 50/28mg versus 12 mg Group from 232SM203

### 6.6.1. Change in CSF NF-L from (ratio to) baseline to Day 279

The analysis will be performed on the ITT set but is it noted that neurofilament CSF samples from China sites were not analyzed due to export law complication. The baseline and post baseline results for NF-L for these participants will be imputed in the MI step. Only baseline, Day 29 and Day 279 visits will be included as visits in the MI.

Values that are BLQ will be set to half of the diluted LLOQ (65 pg/mL).

The Neurofilament light chain (NF-L) CSF concentration change (including absolute and ratio to baseline) will be presented by visit.

Summary tables and LS-mean (+- 95% CI) plots for geometric mean ratio to baseline using MI data and ANCOVA will be presented.

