## 2.2. Study Design

This 3-part study will evaluate the efficacy and safety of a high dosing regimen of nusinersen in approximately 145 participants. The study will be conducted at approximately 65 sites globally. Following the completion of this study, all eligible participants may elect to enrol in a separate long-term extension study (232SM302), pending study approval by ethics committees and the appropriate regulatory authorities. In regard to participants rolling over from Part B, this will be done without unblinding the participant's treatment group.

Part B will consist of a pivotal, double-blind, active-controlled treatment period with either 2 or 4 loading doses of nusinersen (for the 50/28 mg Group and Control Group, respectively) administered intrathecally followed by maintenance doses approximately every 4 months thereafter. Approximately 75 participants with infantile-onset SMA will be randomized in a 1:2 ratio to receive either the currently approved dosing regimen or a 50/28 mg dosing regimen.

In the Control Group, up to a total of 25 participants will receive 4 loading doses of 12 mg of nusinersen administered intrathecally (Days 1, 15, 29, and 64), followed by maintenance doses of 12 mg on Days 183 and 279 (and a sham procedure on Day 135).

Product: Nusinersen	Statistical Analysis Plan
Study: 232SM203	Version: 3.0 Final

In the 50/28 mg Group, up to a total of 50 participants will receive 2 loading doses of 50 mg of nusinersen administered intrathecally (Days 1 and 15) and 2 sham procedures on Days 29 and 64, followed by maintenance doses of 28 mg on Days 135 and 279 (and a sham procedure on Day 183). In order to maintain blinding sham procedures will be used as shown in the table below.

Arm	Dose 1	Dose 2	Dose 3	Dose 4	Dose 5	Dose 6	Dose 7
50/28 mg	D1	D15	D29	D64	D135	D183	D279
Group	(50 mg)	(50 mg)	(sham)	(sham)	(28 mg)	(sham)	(28 mg)
Control (12/12	D1	D15	D29	D64	D135	D183	D279
mg) Group	(12 mg)	(12 mg)	(12 mg)	(12 mg)	(sham)	(12 mg)	(12 mg)

Participants will remain at the clinic for at least 24 hours after each study treatment administration or sham procedure.

Randomization in Part B will be performed using interactive response technology (IRT) and the randomization will be stratified by disease duration as follows:

- $\leq$  12 weeks and
- > 12 weeks (time from age at symptom onset to age at informed consent)

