### 7.1.8. LP opening pressure

LP opening pressure will only be measured at Days 1, 15, and 279 to avoid potential unblinding. A lack of published data exists in terms of the variability of opening pressure between and within subjects. It is suspected that a simple change in position of a subject during the measurement or change of instrument used contributes to variability in the measurement.

[figure not shown]

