## Summary of Changes from the Previous Version 1.0 of the SAP

Added in the per protocol set definition: Participants who had a previous diagnosis that would confound the data/conflict with SMA.

Added text to Section 6.4.1 to clarify that if baseline is missing, the median used in the imputation will be rounded up to the nearest integer value.

Added clarification to Section 6.4.3 that Ranking based on death will be performed as described earlier for CHOP INTEND. In terms of ranking based on the NF-L, progressively higher ranks will be given to subjects with a greater reduction in NF-L at Day 183.

Removed the analysis of CSF NFL with the joint rank test at Day 64 in Section 6.6.1. Day 64 is not feasible to use since the 50/28mg received a sham procedure at Day 64.

Two sensitivity analyses added to Section 6.1 based on comments from the FDA:

- Use of an ANCOVA model where the variance is estimated in each treatment arm separately for the main analyses of the change in CHOP INTEND and HINE-2 total score to Day 183 comparing sham to Higher dose.
- Implementation of Jump To Reference (J2R) and the joint rank test for the main analyses of CHOP INTEND and HINE2 total score for sham compared to higher dose and 12mg compared to higher dose.

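### The CSF NF-L imputation includes Day 29, a sham day for the 50/28 mg arm, so one arm has no data at that visit and its Day 29 treatment parameter cannot be estimated

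*SAP*

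**What the plan says.** All references are to the Part B infantile-onset SAP, version 3.0.

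- **Section 6.6.1** (change in CSF NF-L to Day 279, 50/28 mg versus 12 mg): "Only baseline, Day 29 and Day 279 visits will be included as visits in the MI". It also says that China-site CSF samples were not analysed and that those participants' results, baseline included, will be imputed. It plans concentration change by visit, and summary tables and LS-mean plots from imputed data with ANCOVA.
- **Section 2.2**, 50/28 mg arm: "and 2 sham procedures on Days 29 and 64, followed by maintenance doses of 28 mg on Days 135 and 279". Section 2.2, 12 mg arm: "4 loading doses of 12 mg of nusinersen administered intrathecally (Days 1, 15, 29, and 64"), then maintenance doses on Days 183 and 279.
- **Summary of changes from version 1.0**, explaining why a CSF analysis was removed from Section 6.6.1: "Day 64 is not feasible to use since the 50/28mg received a sham procedure at Day 64".
- **Section 7.1.8**: "LP opening pressure will only be measured at Days 1, 15, and 279 to avoid potential unblinding".
- **Section 6.1**: one MCMC imputation model with treatment arm, disease duration, baseline and post-baseline values as variables, 100 imputations, and acceptance when relative efficiency is about 98% or more. For NF-L, values are on the log scale and only a lower limit is set for imputed values.

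**The concern.** The reason given for excluding Day 64 applies equally to Day 29: the 50/28 mg arm has a sham on both days. One sham day was taken out of the CSF analysis and the other is named in the imputation visit list.

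Two things are at stake. First, a visit that is empty in one arm enters a joint model with treatment as a variable, so one parameter has no information and the chain can wander along it. Second, if means from the imputed data are tabulated or plotted at every visit in the model, the report would show a Day 29 geometric mean ratio and confidence interval for 50/28 mg with no observed Day 29 value behind them. Nothing in Section 6.6.1 would stop this or flag it.

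**Working it through.** The SAP gives no figure for this point, so there is none to reproduce.

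**1. Days with an intrathecal dose in both arms** (dosing table, Section 2.2)

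| Day | 1 | 15 | 29 | 64 | 135 | 183 | 279 |
|---|---|---|---|---|---|---|---|
| 50/28 mg | dose | dose | sham | sham | dose | sham | dose |
| 12 mg | dose | dose | dose | dose | sham | dose | dose |

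The common days are 1, 15 and 279. The only common post-baseline days are 15 and 279.

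**2. Amount missing at Day 29.** Section 2.2 gives arm sizes of up to 50 and up to 25. Missing by design: 50/50 in the 50/28 mg arm, and 50/75 = 66.7% overall, before any China-site loss (number not given).

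**3. Estimability.** Regress Day 29 on intercept, treatment, disease duration and baseline. Every observed row is a 12 mg row, so treatment is constant there. The design has rank 3 of 4 and the treatment coefficient cannot be estimated. With a visit observed in both arms the rank is 4 of 4.

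Day 279 is different. Its regression on treatment, baseline and disease duration is supported by observed Day 279 values in both arms. How the treatment effect splits into a part passing through Day 29 and a remainder is unknown, but their sum is identified, and the Day 279 contrast needs only the sum.

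**4. Simulation of the planned imputation.** Joint normal model with treatment as a variable, Jeffreys prior, 200 burn-in iterations, 100 imputations taken 100 iterations apart, N = 50 + 25, three seeds. Assumed, not from the SAP: about 10% with no NF-L at all (China sites), about 10% further missing at Day 279, and residual SD 0.4 to 0.5 on the log scale. The analysis model adjusted for baseline and disease duration. The true adjusted effect at the interim visit was -0.3.

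| Seed | Interim visit | Range of imputed arm difference at that visit | Fraction of missing information at that visit | Day 279 estimate (SE) |
|---|---|---|---|---|
| 1 | absent in 50/28 mg | -7.48 to 1.55 | 0.998 | -0.47 (0.11) |
| 1 | in both arms | -0.28 to -0.09 | 0.094 | -0.47 (0.11) |
| 2 | absent in 50/28 mg | -5.39 to 2.87 | 0.996 | -0.40 (0.13) |
| 2 | in both arms | -0.42 to -0.34 | 0.019 | -0.44 (0.13) |
| 3 | absent in 50/28 mg | -2.08 to 3.16 | 0.996 | -0.35 (0.13) |
| 3 | in both arms | -0.27 to 0.01 | 0.136 | -0.31 (0.13) |

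The Day 279 shifts are 0.00, 0.04 and 0.04 log units, with equal standard errors.

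A second simulation assumed 15% with no NF-L and 10% further missing at Day 279. Its Day 279 estimates with Day 29, with Day 15 and with no interim visit were -0.392, -0.412, -0.396; -0.432, -0.455, -0.456; and -0.518, -0.512, -0.478. The largest shift caused by using Day 29 is 0.518 - 0.478 = 0.040. The two sound choices differ from each other by up to 0.512 - 0.478 = 0.034.

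**5. The acceptance check.** Relative efficiency = 1/(1 + γ/m), where γ is the fraction of missing information. With m = 100 and γ = 1 it is 1/1.01 = 0.990. Falling below 0.98 would need γ > 100 × (1/0.98 - 1) = 2.04, which is impossible because γ cannot exceed 1.

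**The case against.** The strongest reply is that the named endpoint, change to Day 279, is not harmed. That stands. A reader might infer that the whole imputation model is unidentified and the Day 279 comparison invalid, but steps 3 and 4 do not support this. The shift from using Day 29 is about as large as the difference between two acceptable visit lists.

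Three other strong readings also go too far:

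- **That the SAP plans a Day 29 LS mean for 50/28 mg.** In Section 6.6.1 the by-visit wording belongs to the sentence on concentration change. The sentence on imputed data and LS-mean plots names no visits. A Day 29 mean is a plausible output, not a stated one.
- **That the chain must fail, or drift by a particular amount.** The drift is random movement of a parameter with no data, under assumed missingness. Its width differs by seed and is not an effect size.
- **That Day 29 makes the relative-efficiency check useless.** With 100 imputations the check passes whatever visits are used. It fails to detect this fault but is not broken by it.

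It is also fair to say that no CSF sampling table is shown. That no CSF is taken at a sham is inferred from the SAP's stated reason for dropping Day 64. Section 7.1.8 concerns opening pressure and gives unblinding as its reason, so it agrees with the common days but is not a CSF schedule. The change summary is cited here for its reasoning, not as text in conflict with the current plan.

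The common-visit rule and the convergence fallback in Section 6.1 do not answer the point. Both are written for comparisons with historical controls.

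**Conclusion.** The point holds in limited form. The Section 6.6.1 visit list conflicts with the Section 2.2 dosing schedule and with the SAP's own reason for excluding Day 64. Day 29 CSF NF-L is missing by design in up to 50 of 50 participants on 50/28 mg, and the Day 29 treatment parameter cannot be estimated. The Day 279 comparison remains identified and moved by about 0.04 log units or less in simulation.

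The practical risk is drift or non-convergence and, if imputation-based means are shown by visit, a Day 29 ratio for 50/28 mg with no observed Day 29 data. Neither the relative-efficiency check nor the lower limit on imputed NF-L would reliably reveal it.

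The conclusion rests on one inference, that a sham yields no CSF. The simulated sizes rest on assumed missingness and variances. Severity is moderate: CSF NF-L is a secondary endpoint outside the 11 ranked tests in Table 2, and the two ranked NF-L tests use plasma.

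**What to change.** In Section 6.6.1, remove Day 29 from the imputation visit list and use baseline and Day 279 only. Day 15 may be added if CSF NF-L was assayed then in both arms, which the sampling schedule must confirm. Day 29 may be a slip for Day 15, but the document does not say so.

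Add one sentence: imputation-based between-arm CSF NF-L results are presented only for visits with CSF in both arms. Observed Day 29 values in the 12 mg arm can still be summarised descriptively.

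The cost is a sentence or two in the SAP and one line of imputation code. Trial conduct and the ranked tests are unchanged.

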### 6.6.2. Number and Length of Hospitalizations

The number of hospitalizations during the study will be analyzed using the rate at which they occur. For descriptive purposes, the aggregate hospitalization rate will be calculated for each group by dividing the total number of hospitalizations that occurred in the group by the total number of subject-years on study.

Annualized hospitalization rate will be calculated for each subject as the number of hospitalizations that the subject experienced divided by the number of days on study and this ratio multiplied by 365.25. Annualized hospitalization rate will be analyzed by a negative binomial regression model, adjusted for disease duration at screening and baseline CHOP INTEND total score. The logarithmic transformation of the time on the study will be included in the model as the "offset" parameter. If the data are under dispersed, or if the negative binomial regression model does not converge, a Poisson regression model with the same covariate will be used instead of the negative binomial regression model. Dispersion will be evaluated from the Pearson chi-squared statistic.

For each subject, the total time spent in hospital during the study will be calculated and prorated according to number of days on study. Based on the prorated time in hospital, treatment groups will be compared to an analysis of covariance adjusting for each subject's disease duration at Screening and baseline CHOP INTEND total score.

Analyses will be performed on the ITT Set.

Product: Nusinersen	Statistical Analysis Plan
Study: 232SM203	Version: 3.0 Final

## 6.6.3. Clinical Global Impression of Change (CGIC) [Physician, Caregiver] at Day 302

CGIC will be assessed at Days 29, 64, 183 and 302. The CGIC rating scale was developed as a brief standalone assessment of the clinician's view of the participant's global functioning after initiating a study medication [Guy 1976]. The CGIC provides an overall clinician-determined summary measure that takes into account all available information, including knowledge of the participant's history, psychosocial circumstances, symptoms, behavior, and the impact of the symptoms on the participant's ability to function. The CGIC is administered by an experienced clinician who is familiar with the disease under study and the likely progression of treatment. The clinician makes a judgment about the total picture of the participant at each visit: the severity of the illness, the participant's level of distress and other aspects of impairment, and the impact of the illness on functioning. The CGIC is rated without regard to the clinician's belief that any clinical changes are or are not due to medication and without consideration of the etiology of the symptoms.

The CGIC is a 7-point scale that requires the clinician to assess how much the participant's illness has changed relative to a baseline state at the beginning of the intervention and is rated as follows: 1, very much improved; 2, much improved; 3, minimally improved; 4, no change; 5, minimally worse; 6, much worse; or 7, very much worse.

CGIC should be assessed consistently by the same rater for each study participant. A separate CGIC assessment will be performed by the Investigator (Principal Investigator or Sub investigator) and caregiver.

Clinical Global Impression of Change (CGIC) for the physician and caregiver at Day 302 will be analyzed as an ordered categorical score and as a dichotomized response: "much improved" or "very much improved" versus other responses.

The proportion of subjects with each CGIC score and with the dichotomized response of either "much improved" or "very much improved" will be summarized by visit and treatment group.

The difference in CGIC dichotomized response rate between 50/28 mg Group and Control Group will be analyzed using a logistic regression model with terms for treatment group and disease duration at screening and baseline CHOP INTEND total score. Participants who die or withdraw from the study, prior Day 302, will be counted as 'non responders'.

The odds ratio, its 95% CI and the p-value for 50/28 mg Group compared to the Control Group will be presented. The proportion of CGIC responders at other visits will also be analyzed in a similar way.

Analyses will be performed on the ITT Set.

### 6.6.4. Number of Serious Respiratory Events

All adverse events that are coded into the System Organ Class (SOC) of respiratory, thoracic, and mediastinal disorders, as their primary SOC will be considered respiratory events. Only

Product: Nusinersen	Statistical Analysis Plan
Study: 232SM203	Version: 3.0 Final

those classified as serious will be analyzed. By utilizing the above approach, rare occurrence of serious respiratory events in the Infection and Infestation SOC and Investigation SOC (if any) may not be included. However, a detailed review of the AE listing will be conducted to identify such events.

The number of serious respiratory events during the study will be analyzed using the rate at which they occur. For descriptive purposes, the aggregate rate will be calculated for each group by dividing the total number of serious respiratory events that occurred in the group by the total number of subject-years on study.

Annualized serious respiratory event rate will be calculated for each subject as the number of serious respiratory events that the subject experienced divided by the number of days on study and this ratio multiplied by 365.5.

Although serious respiratory events occur as a stochastic process and can be assumed to be from a Poisson distribution, studies in other therapeutic areas have shown that data of this type are typically over-dispersed, i.e., the variation seen is greater than that predicted by the Poisson model. To account for over-dispersion in the annualized rate of serious respiratory events, the negative binomial distribution will be used. Thus, on the basis of annualized serious respiratory event rate, treatment groups will be compared using a negative binomial model adjusting for disease duration at Screening and baseline CHOP INTEND total score. An "offset" parameter, the logarithm of the time on study, will be included in the model. If the data are under dispersed, or if the negative binomial regression model does not converge, a Poisson regression model with the same covariate will be used instead of the negative binomial regression model. Dispersion will be evaluated from the Pearson chi-squared statistic.

Analyses will be performed on the ITT Set.

### 6.6.5. Proportion of Time on Ventilation

The ventilation use during the study will also be collected via the daily ventilation diary. Daily ventilation use data that are missing will be imputed using the greater of the days that flank the missing day(s).

For each subject, the total number of hours of ventilation support required during the study will be calculated and prorated according to number of days on study. Based on the prorated number of hours of ventilation support, treatment groups will be compared via an analysis of covariance adjusting for each subject's disease duration at Screening and baseline CHOP INTEND total score.

An additional analysis of the number of days in which each subject required ventilation support of  $\geq 16$  hours per day will be performed. The number of days that this level of ventilation was required will be analyzed by analysis of covariance adjusting for each subject's disease duration at Screening and baseline CHOP INTEND total score.

Analyses will be performed on the ITT Set.

Product: Nusinersen	Statistical Analysis Plan
Study: 232SM203	Version: 3.0 Fina

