## 5.3. Demographic and Baseline Characteristics

Baseline data (demography, medical history, SMA history, and baseline disease characteristics) will be summarized.

Formal statistical analyses will not be done to test for homogeneity between treatment groups. If there are apparent heterogeneities between the groups in any of the participant characteristics that are of clinical importance or could affect the treatment outcome, the impact of the imbalances will be investigated and, if appropriate, adjustments made in the efficacy and safety analyses.

Demography includes age at screening, age at first dose, sex, ethnicity, race and country,

Medical history will be coded in MedDRA and the number and percentage of subjects with each medical history presented by preferred term.

SMA history will include gestational age, birth weight, age at symptom onset, time from disease onset to enrollment, age at SMA diagnosis, history of SMA symptoms (hypotonia, developmental motor delay, paradoxical breathing, pneumonia or respiratory symptoms, limb weakness, swallowing or feeding difficulties, and other symptoms), and the number of copies of the SMN1 and SMN2 gene.

Baseline disease characteristics will be assessed by CHOP INTEND total score, total HINE Section 2 motor milestones, and growth parameters - these assessments are further described in Section 6. If a participant was receiving ventilation at Day 1, then the number of hours of ventilation use on Day 1 will also be summarized as baseline. In addition, use of a gastrointestinal tube will be presented. Use of gastrointestinal tube will be determined from either medical history or as a procedure prior to first dose coded as 'Gastrostomy' or 'Gastrointestinal tube insertion'.

Product: Nusinersen	Statistical Analysis Plan
Study: 232SM203	Version: 3.0 Final

Demographic and baseline disease characteristics will be presented for the ITT Set, the PPS, the Safety Set as appropriate. Additional presentations will be presented to facilitate comparisons at baseline for the planned efficacy comparisons. For example, for the primary endpoint to compare the higher dose to CS3B sham control.

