# 6. Efficacy Endpoints

## 6.1. General Analysis Methods for Efficacy Endpoints

## **Multiple imputation (MI)**

Product: Nusinersen	Statistical Analysis Plan
Study: 232SM203	Version: 3.0 Final

The multiple imputation method [Schafer 1997, Schafer 1999] will be used for participants who discontinue for a reason other than death or have a missing efficacy result at the timepoint of interest. This will be performed for CHOP INTEND, HINE Section 2 total score and NF-L. Any imputation on an item level within a scale for CHOP INTEND and HINE section 2 will be performed prior to performing MI.

The imputations will be performed on total scores. All available data will be used i.e., where subjects have missed doses but continued to perform assessments; otherwise, any missing values will be imputed using MI. In a situation where historical data is used as the control group only the visits which are common between the two groups will be utilized. For example, for the CS3B sham control versus higher dose comparison only the Day 64, Day 183 and Day 302 visits will be included in the list of post baseline visits.

In this situation if convergence issues occur then only the Day 64 and Day 183 post baseline visits will be included.

The Markov Chain Monte Carlo (MCMC) method will be used to impute the missing score.

The treatment variable will be coded so that the Higher dose group is the first in the sort order. Prior to the Proc MI step the dataset will be sorted by treatment and then ascending unique subject identifier (USUBJID). The variable list in the model for imputations will include:

- treatment group, disease duration, baseline value for the endpoint, and all available post baseline values
- For NF-L, the log of baseline and post-baseline values will be used in the PROC MI step.

A set of 100 complete imputed datasets will be generated and the relative efficiency parameter will also be checked to determine the acceptability of the imputed results i.e. it should be close to 98% or higher. The seed used for the multiple imputation for CHOP INTEND will be 5846892, for HINE section 2 Motor Milestones will be 8746890 and for NF-L will be 7635789.

If the MI procedure imputes any values outside the expected range for the scale, e.g. from 0 to 64 for CHOP INTEND, then values below 0 will be set to 0 and values above 64 will be set to be 64. For NF-L if any imputed values are  $< \log(LLOQ)$  then set as  $\log(LLOQ/2)$ .

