## ANCOVA model

For each of the 100 imputed datasets, the endpoint will be compared between treatment groups using an ANCOVA model for continuous endpoints (primary, secondary and NF-L endpoints). The ANCOVA model will include covariates for each of the corresponding baseline value for the endpoint, baseline CHOP INTEND total score (if not the endpoint under consideration) and disease duration at informed consent. The model will be used to present overall LS means and standard errors for each treatment group, and LS mean differences for treatment with corresponding 95% CI.

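### The two ventilation ANCOVAs in section 6.6.5 omit baseline ventilation hours: a minor, nearly free gain in precision is left unused

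*SAP*

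**What the plan says.** All references are to the Part B infantile-onset SAP.

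- **Section 6.6.5** takes total ventilation hours prorated by days on study: "Based on the prorated number of hours of ventilation support, treatment groups will be compared via an analysis of covariance". Only two covariates enter that model, which is described as "adjusting for each subject's disease duration at Screening and baseline CHOP INTEND total score". A second ANCOVA, of days needing at least 16 hours of support, has the same two covariates. Both use the ITT Set and compare 50/28 mg with 12 mg.
- **Section 5.3** says that, for a participant ventilated at Day 1, "the number of hours of ventilation use on Day 1 will also be summarized as baseline". It adds that if clinically important heterogeneity is apparent, "the impact of the imbalances will be investigated and, if appropriate, adjustments made in the efficacy and safety analyses".
- **Section 6.1, ANCOVA model**, gives the general rule: "The ANCOVA model will include covariates for each of the corresponding baseline value for the endpoint". It is written for the 100 imputed datasets. The multiple imputation text limits their scope: "This will be performed for CHOP INTEND, HINE Section 2 total score and NF-L".
- **Section 2.2** gives the design: "Approximately 75 participants with infantile-onset SMA will be randomized in a 1:2 ratio", that is 25 on 12 mg and 50 on 50/28 mg. On balance it says "the randomization will be stratified by disease duration as follows". No other stratification factor is named.

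**The concern.** How much ventilation an infant needs at entry is a natural candidate predictor of how much the infant uses on study. The plan recognises this quantity as a baseline characteristic but does not use it in the model of the matching outcome. Disease duration and CHOP INTEND may capture part of it, but neither measures respiratory support.

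Two things are at stake. First, any variation in on-study hours that baseline hours would explain stays in the residual and widens the confidence interval. Second, randomisation is not stratified on ventilation and the smaller arm has 25 infants. The arms can therefore differ at entry by chance, and the estimated dose difference then carries part of that gap. As an illustration, one infant on an assumed 12 hours a day throughout adds 12/25 = 0.48 hours a day to the mean of the smaller arm, or 12/50 = 0.24 to the larger.

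**Working it through.** **The plan's own figure.** The SAP states no power, SD or effect for ventilation hours. Its only power statement (section 2.3) is for the primary endpoint: 50 versus 20, 24 points, SD 8.8, at least about 99%. That reproduces: 24 / (8.8 × √(1/50 + 1/20)) = 24 / 2.328 = 10.3 standard errors, so power is essentially 1.00. It has no bearing on section 6.6.5.

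**Inputs from the SAP.** The arms are 25 and 50. Two-sided 0.05 is the SAP's programme-wide level and is used here for illustration, since this endpoint has no allocated alpha.

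**Assumed input.** rho is the partial correlation of baseline hours with prorated on-study hours, given disease duration and CHOP INTEND. The documents give no value, so a range is shown.

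**Precision.** In units of the residual SD without the term, SE = √(1/25 + 1/50) = √0.06 = 0.245. Adding the covariate multiplies the variance by (1 − rho²), apart from one degree of freedom. An equivalent total N is 75 / (1 − rho²). For an effect with 80% power without the term, power with it is Φ(2.802/√(1 − rho²) − 1.96), where 2.802 = 1.960 + 0.842. For a 50% start, 1.960 replaces 2.802.

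| rho | 1 − rho² | SE change | Equivalent N | Power from 80% | Power from 50% |
|---|---|---|---|---|---|
| 0.1 | 0.99 | −0.5% | 75.8 | 80.4% | 50.4% |
| 0.3 | 0.91 | −4.6% | 82.4 | 83.6% | 53.8% |
| 0.5 | 0.75 | −13.4% | 100 | 89.9% | 61.9% |
| 0.7 | 0.51 | −28.6% | 147 | 97.5% | 78.4% |

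**Chance imbalance.** If baseline hours differ between arms by k standard errors, the estimate without the term shifts by rho × k × 0.245 SD. The test statistic under no effect then has mean rho × k and variance 1 − rho².

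| rho | Shift at k = 1 (SD) | Conditional type I error, k = 1 | Conditional type I error, k = 1.96 |
|---|---|---|---|
| 0.1 | 0.02 | 5.0% | 5.3% |
| 0.3 | 0.07 | 5.0% | 7.9% |
| 0.5 | 0.12 | 4.8% | 12.9% |
| 0.7 | 0.17 | 3.9% | 20.5% |

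A one-SE imbalance does not inflate the error rate. An imbalance of 1.96 SE does, but one that large or larger arises in only 5% of randomisations. Averaged over all randomisations the rate is 5%.

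**Many zeros.** Hours may well be zero for many infants, so a zero-inflated simulation was also run. Its inputs are assumed: nominal shares ventilated at baseline of 5%, 10%, 20%, 30% and 40%, with use largely persisting on study. The variance ratio with versus without the term was 0.90, 0.85, 0.71, 0.63 and 0.61. From binomial sampling at those shares, a between-arm gap of 10 percentage points or more arises in about 9%, 22%, 36%, 42% and 45% of trials.

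**The case against.** There are five arguments for leaving section 6.6.5 alone.

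- **It follows a local convention.** A reader might infer that these are the only continuous efficacy ANCOVAs without an own-baseline term. The documents do not support that: the ANCOVA of prorated hospital time in section 6.6.2 also adjusts only for disease duration and CHOP INTEND. However, the SAP defines no baseline for hospital time, whereas for ventilation it does. The contrast that stands is with CHOP INTEND, HINE Section 2 and NF-L.
- **The general rule may already cover it.** The ANCOVA paragraph in section 6.1 mentions secondary endpoints, and proportion of time on ventilation is one (section 2.1). But the paragraph is written for the imputed datasets, ventilation is not among the imputed endpoints, and section 6.6.5 has its own diary imputation and its own covariate list. The two places can be read differently and should be reconciled.
- **Section 5.3 provides for imbalance.** It does, but only after the data are seen and with no model fixed. That does not replace a prespecified term.
- **Nothing is invalid.** A reader might infer that the model wrongly credits baseline imbalance to dose, so that the comparison is biased. Treatment is randomised and unconditional type I error is 5%, so the issue is efficiency and conditional bias only.
- **The benefit is unproven and the Day 1 value is not clean.** Both points stand. A definite power gain cannot be claimed, because rho and the share ventilated at entry are unknown. Section 3.6.1 lists permanent ventilation or tracheostomy at Screening as a significant deviation, which suggests a restricted range of baseline hours, although the 6.6.5 analyses use the ITT Set. Section 3.1 defines Study Day 1 as the date of first dose, so Day 1 hours may include use after dosing.

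**Conclusion.** The point holds as a minor one. Section 6.6.5 omits a baseline value that the plan already summarises, and neither the general ANCOVA rule nor the imbalance provision clearly supplies it. The direction is certain for any appreciable partial correlation: a smaller residual variance and less exposure to chance imbalance. The size cannot be determined from the documents. From an 80% start, power rises by less than half a point at rho 0.1, about 4 points at 0.3 and about 10 at 0.5. All three values of rho are assumptions, and the power formula ignores the lost degree of freedom and assumes roughly normal estimates. If few infants are ventilated at entry, the gain is small.

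The randomised test is sound as written. The endpoint lies outside the 11-step sequence of Table 2, so no confirmatory claim depends on it.

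**What to change.** In section 6.6.5, add baseline ventilation hours per day (0 if not ventilated) as a covariate in both ANCOVAs, beside disease duration and baseline CHOP INTEND. Define it from use before the first dose and name the source record, so that no post-dose Day 1 hours enter. State in section 6.1 whether the own-baseline rule extends to the endpoints of section 6.6, so that the two sections agree.

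The cost is a few lines of SAP text and one model degree of freedom. No new endpoint data are needed. The sponsor should confirm that a pre-dose figure can be separated from the Day 1 record or taken from an earlier one, since the SAP does not show this.
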